Fasting Versus Non-fasting prior to elective Cardiac catheterisation

Chief Investigator: [name]

Principal Investigator: [name]

Research Trust: Blackpool Teaching Hospitals NHS Foundation Trust

Funder: Blackpool Teaching Hospitals NHS Foundation Trust

Sponsor: Blackpool Teaching Hospitals NHS Foundation Trust

Date of Submission: 12/10/2017

Table of Contents

1	STUDY SUMMARY	4
2	INTRODUCTION	6
2.1	BACKGROUND.....	6
2.2	STUDY OBJECTIVES.....	8
3	STUDY DESIGN	9
3.1	GENERAL	9
3.2	STUDY PROCEDURE.....	9
3.3	PRIMARY STUDY ENDPOINTS	10
3.4	SECONDARY STUDY ENDPOINTS	10
3.5	END OF STUDY	10
4	METHODS	10
4.1	SUBJECT SELECTION AND WITHDRAWAL.....	10
4.1.1	Inclusion Criteria	11
4.1.2	Exclusion Criteria	11
4.2	SUBJECT RECRUITMENT AND SCREENING	11
4.3	RANDOMISATION PROCESS	11
4.4	INFORMED CONSENT.....	12
4.5	WITHDRAWAL OF SUBJECTS	12
5	PRIOR AND CONCOMITANT THERAPY	12
6	CLINICAL PROCEDURES	12
7	STATISTICAL PLAN	12
7.1	SAMPLE SIZE DETERMINATION	13
7.2	STATISTICAL METHODS	13
7.3	INTERIM ANALYSES	13
7.4	SUBJECT POPULATION(S) FOR ANALYSIS	13
8	SAFETY AND ADVERSE EVENTS	13
8.1	RECORDING OF ADVERSE EVENTS	14
8.2	EXPECTED NON-SERIOUS ADVERSE EVENTS	14
8.3	SERIOUS ADVERSE EVENTS (SAEs).....	14

8.4	EXPECTED SERIOUS ADVERSE EVENTS	15
8.5	UNEXPECTED AND FATAL SERIOUS ADVERSE EVENTS.....	15
8.6	PERIOD FOR RECORDING SERIOUS ADVERSE EVENTS.....	15
9	DATA HANDLING AND RECORD KEEPING	16
9.1	CONFIDENTIALITY	16
9.2	CASE REPORT FORMS.....	16
9.3	RECORDS RETENTION.....	16
10	STUDY MONITORING, AUDITING, AND INSPECTING	17
11	ETHICAL CONSIDERATIONS.....	17
11.1	PATIENT INFORMATION SHEETS	18
12	FUNDING.....	18
13	SPONSORSHIP	18
14	PUBLICATION PLAN.....	18
15	REFERENCES.....	19

1 Study Summary

Title	Fasting Versus Non-fasting prior to elective Cardiac catheterization
Short Title	Fasting or no fasting before cardiac catheterization
Version & Date	Version 1.7 12 October 2017
Principal Investigator	[name]
Objectives	To show that there is no increased risk of peri-procedural complications between fasting and non-fasting patients as well as improved patient satisfaction when allowed to eat up to the point of elective coronary angiography/angioplasty compared to patients kept nil by mouth. We aim to
Methodology / Design	Prospective single centre, single blinded (investigator) randomized Study Consented patients will be randomised in 1:1 ratio to either standard hospital fasting policy or allowed to eat freely up to the point of transfer to the Catheter Laboratory.
Duration	12 months
Participating Centres	Blackpool Victoria Hospital
Primary End Point	Composite of nausea, vomiting, abdominal pain, emergency endotracheal intubation and aspiration,
Number of participants	400 patients
Main Inclusion /Exclusion Criteria	INCLUSION

	
1. All patients >18 years undergoing elective coronary angiography or angioplasty procedures in the 2 months window.
 
EXCLUSION
 
 1. Patient choice 2. Other cardiac procedures such as EP studies, pacing, structural heart disease intervention 3. Emergency PPCI 4. Patients already admitted in the hospital with UA / NSTEMI 5. Patients unable to give informed consent

Statistical Methodology and Analysis
	
Our composite primary endpoint will be analysed using 95% confidence interval between the fasting and non-fasting group using the Fisher's exact test. Categorical secondary outcomes will be presented as number and percentages and compared between the two groups using the Chi-square test or Fisher's exact test. Secondary continuous outcomes will be presented as mean and standard deviation and compared using the independent samples t-test. P-values will be used to assess evidence of difference. P value <0.05 will be considered significant.

2 Introduction

This document is a research protocol and this study will be conducted in compliance with the protocol, The Research Governance Framework, International Conference on Harmonisation, Good Clinical Practice Guideline ICH/GCP, and all applicable Blackpool Teaching Hospitals NHS Foundation Trust Research Office requirements.

This study aims to demonstrate that pre procedural fasting for elective cardiac procedures is unnecessary and outdated practice. It is without doubt that induction of general anaesthesia depresses cough and swallow reflexes and therefore increases the risk of aspiration with airway manipulation. However, coronary angiography and angioplasty does not require general anaesthesia and is carried out purely under local anaesthetic. So why do we still need periods of fasting?

2.1 Background

Nil by mouth (NBM) has been the standard of care for cardiac catheterization since its inception, because of the associated vomiting that was common with the first generation of radio contrast materials that were almost toxic and use of general anaesthesia. Induction of anaesthesia depresses the cough and swallow reflex thus increasing the risk of aspiration, this is also true for deep sedation.

Today, the cardiac catheterization procedure is done under local anaesthesia with anxiolytic sedatives often used peri-procedurally to achieve minimal sedation whereby verbal contact is maintained. Both the royal college of anaesthetists and the royal college of emergency medicine state that fasting is not required for minimal or conscious sedation but does recommend fasting for general anaesthesia.^{1,2} There is only 1% risk of needing emergency surgery for percutaneous coronary interventions (PCIs). The risk of developing pulmonary aspiration following emergency coronary artery bypass grafting (CABG) surgery or emergency direct current conversion (DC) in patients without pre-procedural fasting is in the order of 0.001%.³

There was no evidence that the volume or pH of participants' gastric contents differ significantly between fasting and non-fasting population as shown by Brady et al.⁴ In addition, the overall

incidence of nausea and vomiting was reported to be 1% before elective cerebral angiography in a study carried out by Kwon et al⁵ with no significant difference between fasting and non-fasting group.

Hamid et al⁶ recently conducted a retrospective analysis of registry data for 1916 percutaneous coronary intervention (PCI) patients over a 3 years period. None of the patients were kept nil by mouth (NBM) pre-procedure and no patients required immediate endotracheal intubation nor did any develop aspiration pneumonia intra or post procedurally. They concluded in their observational study that patients undergoing PCI do not need to be fasted prior to their procedures.

The American Society of Anaesthesia guidelines discuss this extensively and have concluded that there is no strong relation between fasting, gastric volume, or risk of aspiration. In any case, the patients at highest risk for nausea and vomiting are those who present with ST-elevation myocardial infarction (STEMI), who are not fasting anyway and the need for emergency intubation/CABG remains rare in these patients.

Prolonged unnecessary fasting can often leave patients dissatisfied and add to the discomfort and anxiety of waiting for a procedure. Patients may also choose to miss their usual medications on the morning of the procedure due to restrictions advised with oral intake, increasing the risk of complications such as poorly controlled hypertension and the associated peri-procedural complications.

There is also evidence that patients often choose to fast longer than advised by healthcare professionals. The reasons for this include: misunderstanding by the patient that a longer period of fasting may be more protective, apprehension and loss of appetite before an invasive procedure, or practical problems with timing of the procedure.

It is very important to address this fasting issue as many patients undergo prolonged periods of fasting prior to a procedure and whilst this is not usually a problem for young fit patients, many of the patients do not fall into this category. Many are elderly with multiple co morbidities and thus run the risk of hypoglycaemia and lethargy.

A further consideration has to be that of patient flow through the cardiac unit. If patients have to be NBM for a certain period prior to cardiac catheterisation then it reduces the ability to fill lists at short notice if patients need to be cancelled. If we can demonstrate that this period of NBM is not necessary then we open the door to maximizing the catheter lab as a resource thus reducing length of stay. This improves patient experience along with the associated financial benefits.

Finally, and probably most importantly we feel that the overall patient experience will be improved if patients are allowed to eat up to the point of procedure decreasing the number of hungry, disgruntled patients who complain to nurses.

In essence, there is little evidence available about the benefits of pre-procedural fasting and prospective randomized trials are lacking with no clear guidelines recommendations that advocate the benefit of fasting prior to cardiac catheterization. Therefore, we aim to investigate the safety of this approach by this study.

2.2 Study Objectives

- To show that allowing patients to eat freely up to the point of elective coronary angiography/angioplasty is not associated with any increased risk of nausea, vomiting, abdominal pain, emergency intubation or aspiration pneumonia compared to patients kept nil by mouth.
- To show improved patient satisfaction when allowed to eat up to the point of elective coronary angiography/angioplasty compared to patients kept nil by mouth.

We aim to provide evidence from a prospective study to help the development of guidelines that can be implemented nationally and internationally regarding pre procedural care of cardiac patients.

3 Study Design

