3.3 Primary Study Endpoints

Primary endpoint is a composite of nausea, vomiting, abdominal pain, emergency intubation and aspiration

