3.4 Secondary Study Endpoints

- Patient satisfaction
- Incidence of hypoglycaemia (blood sugar < 3.6 mmol/l) as assessed by finger prick test
- Incidence of hypotension (SBP<90 mmHg and /or DBP<60 mmHg)
- 30 day chest infection rate

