4.5 Withdrawal of Subjects

If any patient chooses to withdraw from the study, they will revert to the standard hospital procedure. However, they will still be included in the final analysis as intention to treat and any drop out or cross over will be documented.

5 Prior and Concomitant Therapy

All previous medication and treatments should continue.

6 Clinical Procedure

As standard practice, operators will be allowed to use any techniques they commonly use throughout their practice (choice of access, balloon and stent type).

7 Statistical Plan

Given that the occurrence of pulmonary aspiration was so low in similar studies performed for cerebral angiography, we decided against using this as a single primary endpoint as thousands of patients would be required. We opted for a composite primary end point of nausea, vomiting, abdominal pain, emergency intubation and aspiration. These will be recorded both immediately intra/post procedure by the operation physician and again by the patient within 8 hours after the procedure. We will compare the two groups using 95% confidence intervals to ascertain the extent to which they overlap. Secondary end points will be overall patient satisfaction, the incidence of hypoglycaemia and hypotension, and 30 day chest infection rate which will be compared between the two groups.

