7.1 Sample Size Determination

With 200 participants in each group, if none of the participants has an event then the upper limit of the 95% confidence interval for event rate would be 1.5%. Hence if both groups, fasting and non-fasting, have no events recorded then it is highly unlikely that the event rate in the two groups would differ by more than 1.5%. Provided that a difference of 1.5% in event rate is deemed not clinically meaningfully different; then 200 participants in each group would demonstrate that not fasting has a similar event rate to fasting.

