9.3 Records Retention

All records will be archived for 5 years in line with the Trust R&D Policy.

10 Study Monitoring, Auditing, and Inspecting

The investigator will permit study-related monitoring, audits and inspections by the Ethics Committee, the Sponsor and the Research Governance Manager.

Participation as an investigator in this study implies adherence to the principles and responsibilities of the Research Governance Framework, ICH/GCP and Directive 2000/20/EC

11 Ethical Considerations

The patient will receive a detailed description of the study in the patient information sheet send together with pre-procedure assessment letter by mail (around 1 week before the pre-procedure assessment clinic date) to give him/her time to think about the study. Then, at the pre-procedure assessment clinic, they will have the opportunity to ask questions with one of the research team and to answer any queries. Any patient will have the right to abstain from taking part into the study or to withdraw after taking part without affecting the standard of care they are receiving.

The Chief Investigator will ensure that the risk of the study does not outweigh the benefit at any point during the study time, and if so, the study will be prematurely terminated.

The benefit /risk of taking part into the study will be adequately explained to the patients. There will be no direct benefit to the patient from taking part in this study. However, the information gained from the study will help improve the quality of service offered to the patients, increase their satisfaction, may aid in changing the current practice and avoiding unnecessary delay to the patients. The potential risk will be made clear which is the occurrence of nausea and vomiting at an expected rate of 1-2% and no expected emergency endotracheal intubation or aspiration pneumonia cases.

Once patient is enrolled in the study, all his personal information will be anonymized with the only identifier the study number. All patient data will be password protected on the computer in the cath lab. All health professionals involved in the study and patient care will have access to this

information if required. Only the CI will have access to identify the patient personal data for the purpose of safety.

To ensure un-biased result, an adequate randomization process with intention to treat analysis will be undertaken. Analysis will be done by the Sub-Investigator who is blinded to group allocation.

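### Section 2.2 sets out to show no added risk of each listed event, including intubation and aspiration pneumonia, but only a composite is analysed, and it says almost nothing about those two

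*Combined protocol and SAP*

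**What the plan says.** All references are to the combined protocol and SAP.

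- **Objective (2.2).** The aim is to show that eating freely "is not associated with any increased risk of nausea, vomiting, abdominal pain, emergency intubation or aspiration pneumonia", compared with being kept nil by mouth. The wording covers each event in the list.
- **Endpoint (3.3).** "Primary endpoint is a composite of nausea, vomiting, abdominal pain, emergency intubation and aspiration". The last component is aspiration, not aspiration pneumonia.
- **Recording (7).** The operator records the components during and just after the procedure, and they are recorded "again by the patient within 8 hours after the procedure".
- **Analysis (7.2).** The composite gets a 95% confidence interval and Fisher's exact test. No analysis or table of the separate components is described.
- **Expected events (11).** The risk to be explained to patients is "nausea and vomiting at an expected rate of 1-2% and no expected emergency endotracheal intubation or aspiration pneumonia cases".
- **Why a composite (7).** On pulmonary aspiration: "we decided against using this as a single primary endpoint as thousands of patients would be required".
- **Later follow-up.** Section 3.4 lists the "30 day chest infection rate" as a secondary endpoint, and section 3.2 plans a phone call on day 30. Section 8.5 lists pulmonary aspiration and emergency endotracheal intubation as unexpected SAEs, and section 8.6 collects SAEs for one month.

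**The concern.** The objective and the analysis do not match. The objective speaks about every listed event, while the analysis yields one comparison of a combined rate. On the protocol's own expectations, the events behind that rate will come from the milder components, and intubation and aspiration will contribute few or none.

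Intubation and aspiration are the harms that fasting is meant to prevent. If the composite shows no difference, a reader of section 2.2 would take it that the trial had shown no added risk of them. The composite can also balance while its parts do not: one more aspiration and one fewer case of nausea in the non-fasting arm leave the total unchanged. Section 2.2 goes on to say that the evidence should inform national and international guidelines, where such a reading would do most harm.

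The change from aspiration pneumonia in 2.2 to aspiration in 3.3 adds a second gap. Pneumonia may be diagnosed after the 8-hour record, and no rule says whether such a case belongs to the composite.

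**Working it through.** **Inputs.** 200 patients per arm (7.1); 1-2% nausea and vomiting, with no intubation or aspiration pneumonia expected (11); Fisher's exact test at p<0.05 (7.2). Sidedness is not stated, so I take Fisher's test as two-sided.

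**1. The plan's own figure.** Section 7.1 says that with no events in 200, "the upper limit of the 95% confidence interval for event rate would be 1.5"%.
- Rule of three: 3/200 = 1.50%.
- Exact one-sided 95% limit: 1 − 0.05^(1/200) = 1.49%.

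Both reproduce the stated figure. The exact two-sided 95% interval (Clopper-Pearson) has upper limit 1 − 0.025^(1/200) = 1.83%. The gap between 1.5% and 1.83% is one-sided against two-sided; it is not an arithmetic error in the plan.

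**2. Expected content of the composite.**
- Nausea and vomiting: 200 × 1% = 2 to 200 × 2% = 4 events per arm.
- Intubation and aspiration pneumonia: none expected.
- Abdominal pain: no rate is given, so its share is unknown.

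**3. What zero serious events would show.** With 0/200 intubations or aspirations in the non-fasting arm, the data remain compatible with a true rate of up to 1.83% (1.49% one-sided), that is, between 1 in 50 and 1 in 100. For events that the protocol does not expect to see at all, that is a very loose bound.

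**4. What Fisher's test could detect.** Suppose a serious component occurred only in the non-fasting arm. With k events against 0 and equal arms, the two-sided p-value is 2 × the product of (200 − i)/(400 − i) for i = 0 to k − 1.
- k = 5: p = 0.061.
- k = 6: p = 0.030.

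Six against none is thus the smallest such split to reach p<0.05. That is 6/200 = 3.0% in one arm, twice the 1.5-point difference discussed in 7.1.

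**5. Where a later aspiration pneumonia would go.**
- *Composite:* section 7 fixes when components are recorded, section 3.3 gives no window, and neither says how to count a case found later.
- *30-day chest infection rate:* it would be caught there, but that endpoint covers any chest infection and has no diagnostic definition.
- *SAE record:* a serious case could appear as pulmonary aspiration (8.5). Since 8.4 also lists infection among expected SAEs, how it would be classed is open.

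Neither of the last two sources enters the primary analysis.

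**The case against.** The plan has a fair defence. Section 7 explains openly why aspiration is not the sole endpoint. The study summary words the objective more broadly, as peri-procedural complications. Sections 12 to 14 call the trial a pilot, with a larger study to follow. These points justify the composite and the sample size. They do not justify wording in 2.2 that promises a result for each event.

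Several stronger readings are tempting, and the documents do not support them.

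- *Pneumonia after 8 hours is excluded from the composite.* The 8 hours is a recording time, not a stated counting rule. The point is ambiguous.
- *A late aspiration pneumonia would be seen only among all chest infections.* Sections 8.5 and 8.6 give a second route, and 8.3 asks for a case description and causality for each SAE.
- *The composite is almost wholly nausea and vomiting.* Without a rate for abdominal pain this cannot be derived. What can be said is that the serious components are expected to add few or no events.
- *The background aspiration risk can be applied to all 400 patients.* The figure that "is in the order of 0.001"% in section 2.1 refers to unfasted patients having emergency bypass surgery or emergency DC conversion. It is not a rate per elective catheterisation, and nothing here rests on it.
- *Phone-reported pneumonia could simply be added to the composite.* Patients know their allocation (4.3), and the call has no case definition or source confirmation.

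**Conclusion.** The point holds in this form: section 2.2 claims more than the planned analysis can show for emergency intubation and aspiration pneumonia. The best possible result, no such event in an arm, bounds the risk only at 1.83% two-sided (1.49% one-sided), and nothing short of 6 against 0 would register on Fisher's test. Sections 7 and 11 already concede the substance.

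These figures rest on 200 analysed per arm and a two-sided Fisher's test; dropout would loosen them. That the serious components add little to the composite rests on the protocol's own expectation in section 11. The handling of cases found after 8 hours is a gap in definition, not a demonstrated loss of events. A reader might infer that the composite must be given up; it need not be. Whether 400 patients suffice for the composite itself is a separate question, not judged here.

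**What to change.** 1. **Section 2.2.** Limit the safety objective to a comparison of the composite rate. Add that intubation and aspiration will be described by arm with exact upper 95% limits, stating whether these are one- or two-sided, and that no conclusion of no increased risk will be drawn for them.
2. **Section 7.2.** Add a table of all five components by arm, with counts and exact 95% confidence intervals, beside the composite result.
3. **Sections 2.2 and 3.3.** Use one term, aspiration or aspiration pneumonia, in both. State that cases found after the 8-hour record are reported by arm from the SAE and 30-day data already planned, separately from the composite.

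The cost is a narrower claim, some rewording and one extra table. No patients or visits are added. Keeping later cases out of the composite avoids the case definition and source confirmation that phone-reported pneumonia would need in a primary endpoint.

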3.1 General

This will be a prospective single centre, single blinded randomized study.

3.2 Study procedure

All patients to be admitted electively for coronary angiography or angioplasty will be given the opportunity to participate. An invitation letter together with patient information leaflet outlining the study will be sent along with the pre-procedure appointment letter to give the patient time to read and think about the study. Once at pre-procedure assessment clinic, the study will be explained further including potential risks and intended outcome and patients concerns will be addressed. Patient will be given the opportunity either to take part in the study or abstain and follow the standard procedure. If the patient agrees then they will sign the consent form and then be randomised in a 1:1 ratio to either the fasting or non-fasting group and be allocated a patient identification number. This will be done at the pre-procedure assessment clinic.

1- Fasting group (current practice): Clear fluids up to the time of the procedure and no food for at least 2 hours before the procedure.

2-Non Fasting Group: Clear fluids and food up to the time of the procedure.

The pre procedure preparation will then be documented in the notes. Intention to treat analysis will be used to avoid the effects of crossover and dropout providing unbiased comparisons among the treatment groups.

The case report form (CRF) will be appended inside the front cover of the notes to be completed on the day of procedure by the operating physician and the remainder completed by the research team. Finally once the patient is ready for discharge they will be asked to complete an anonymous questionnaire relating to their experience and satisfaction.

A database will be composed on an encrypted flash drive and backed up on the catheter lab computer. Only the patient identification number will be included in this but will still be password protected.

All patients will be contacted by phone on day 30 or the nearest working day thereafter to ensure no chest infections.

